4.4.2 Exclusion Criteria

An individual who meets any of the following criteria will be excluded from participation in this clinical trial:

- 1. Experienced a COPD exacerbation in the 4 previous weeks to study enrollment
- 2. Co-diagnosis of asthma by a WCH Respirologist
- 3. Significant co-morbidities that could interfere with program participation, or terminal illness
- 4. Willing to download and use the Epic Care Companion app and has a suitable mobile device to do this
- 5. Pregnancy

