3.0 CLINICAL TRIAL DESIGN

3.1 Overall Design

This pilot study will be a single center, single arm, pilot trial. There will not be a control group. Each participant will complete the 12-week MLHC virtual program, during which time they will also interact with the Care Companion app. Clinical outcomes will then be reassessed at 6 months after study initiation. The trial is expected to last 12 months.

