3.2 Primary Endpoints

Feasibility endpoints:

- MLHC program participation
 - o Number of patients who started program over total offered
 - Number of patients who completed program over total started
 - Number of providers who referred patients to the program over total
- MLCH Care Companion app use
 - Number of times app opened
 - Number of sessions accessed within the app
 - Number of session tasks marked completed
 - Use of other app features (ex: medication reminder notifications)
 - Time spent using the app each time used

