4.2 Participant Recruitment and Screening

We will target a recruitment of 50 patients with physician diagnosed COPD. The patients will be recruited from the WCH Respirology Program clinics (as patients must be followed at WCH in order to use the Epic Care Companion app component). Recruitment will be accomplished through: advertisement posters in the Respirology clinic directing patients to discuss participation with their WCH Respirologist, and referrals from clinicians/circle of care. The potential participant's respirolgist will be the one to determine interest/consent in the participant being contacted for the study.

Participants who have expressed interest in the study will be contacted by study personnel (for example, a research assistant) to discuss potential participation in the study. Patients will not be compensated for their participation.

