4.4 Eligibility Criteria

4.4.1 Inclusion Criteria

The participant must meet all of the inclusion criteria to eligible for this clinical trial:

- 1. Must be deemed to have capacity to provide informed consent;
- 2. Must sign and date the informed consent form;
- 3. Stated willingness to comply with all study procedures;
- 4. Be diagnosed with COPD as per a WCH Respirologist
- 5. Be 40 years or older
- 6. Be a current or ex-smoker
- 7. Have a history of at least 1 COPD exacerbation (requiring prednisone or antibiotic use, or an urgent healthcare visit of any kind) in the previous 12 months

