5.3 Method for Assigning Participants to Treatment Groups N/A – single arm study

5.4 Administration of Study Intervention

MLHC will be delivered virtually through secure videoconferencing software (Zoom) by CREs as detailed above. All onboarding for the virtual program will be completed by the CREs. Upon study consent, patients will also be oriented to the use of the MLHC Care Companion app by study staff virtually or in-person. They will be shown how to download and login to the Epic Care Companion app, and how to navigate through the MLHC materials. Any tech support needed throughout the study will also be provided by study staff at WCH.

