7.4 Statistical Analyses

7.4.1 General Approach

7.4.2 Analysis of the Primary Endpoint(s)

Feasibility endpoints:

- MLHC program participation
 - Number of patients who started program over total offered
 - Number of patients who completed program over total started
 - o Number of providers who referred patients to the program over total
- MLCH Care Companion app use
 - o Number of times app opened
 - Number of sessions accessed within the app
 - Number of session tasks marked completed
 - Use of other app features (ex: medication reminder notifications)
 - Time spent using the app each time used

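### Exclusion criterion 4 is an inclusion condition in the wrong list: as written, it excludes the patients the trial means to enrol

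*Protocol*

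**What the plan says.** Protocol section 4.4.2 opens with the rule "An individual who meets any of the following criteria will be excluded from participation in this clinical trial". The fourth of its five items is "Willing to download and use the Epic Care Companion app and has a suitable mobile device to do this".

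The seven inclusion criteria in 4.4.1 mention neither the app nor a mobile device. The nearest is item 3, "Stated willingness to comply with all study procedures".

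Elsewhere the protocol treats app use as part of what every participant does:

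- Section 3.1: "Each participant will complete the 12-week MLHC virtual program, during which time they will also interact with the Care Companion app".
- Section 5.4, on patients who have consented: "They will be shown how to download and login to the Epic Care Companion app".
- Sections 3.2 and 7.4.2 list app-use measures among the primary endpoints, for example "Number of times app opened" and "Number of session tasks marked completed".
- Section 4.2 explains why recruitment is confined to the hospital's own clinics: "as patients must be followed at WCH in order to use the Epic Care Companion app component".

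The primary objective in 2.1 is likewise the feasibility of the program delivered together with the app.

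**The concern.** Item 4 is worded as a condition a participant should satisfy, but it stands in a list where satisfying any one item bars entry. The eligibility rule therefore says the opposite of what the rest of the protocol needs.

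Two things are at stake. If the text were followed exactly, the trial would enrol people who are unwilling to use the app or cannot use it, and the app half of the primary objective could not be assessed. If staff instead follow the evident intent, every properly enrolled participant meets a written exclusion criterion. The intended device requirement would then exist nowhere in usable form, because no other section makes a suitable device a condition of entry.

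**Working it through.** There is no figure in the plan to reproduce; the check is one of logic. Let W mean willing to use the app and D mean having a suitable device.

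**Inputs.** The any-item rule and item 4 come from 4.4.2, and inclusion criterion 3 from 4.4.1. The need for app users comes from 2.1, 3.1, 3.2, 5.4 and 7.4.2. Section 4.2 is supporting context: it concerns where patients are followed and does not address willingness or device.

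**Rules.**

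- Item 4 as written excludes (W and D), which leaves (not W) or (not D).
- Inclusion criterion 3, if read as covering app use, also requires W. The two together leave (W and not D).
- The intended rule is (W and D).

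| Combination | Item 4 alone | Item 4 with inclusion 3 covering app use | Intended |
|---|---|---|---|
| Willing, device | excluded | excluded | eligible |
| Willing, no device | eligible | eligible | not eligible |
| Unwilling, device | eligible | not eligible | not eligible |
| Unwilling, no device | eligible | not eligible | not eligible |

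The one combination the trial wants is excluded in both as-written columns, so the overlap with the intended set is empty on either reading. The rows are not equally common and the protocol gives no frequencies, so the table shows which sets are eligible, not how many patients fall in each.

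**Endpoints under the literal reading.** Section 3.2 lists 3 participation ratios and 5 app-use items, 3 + 5 = 8. The 3 ratios could still be counted. The 5 app-use items would be essentially empty: counts at or near zero, and time per use undefined where there is no use. The qualification is needed because an unwilling patient with a device could still open the app.

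**Consequence under the realistic reading.** If staff reverse the rule, up to 50 of the 50 planned participants meet item 4. Three other sections then apply:

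- Section 10.2 allows no deviation or change without ethics board approval, and sponsor agreement as required, unless to remove an immediate hazard.
- Section 11.1 has monitoring check conduct against the currently approved protocol.
- Section 4.7.1 lets an investigator withdraw a participant found to meet an exclusion criterion that precludes further participation, so the error can reach beyond screening.

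**The case against.** The strongest reply is that nobody will be misled. Sections 2.1, 3.1, 3.2 and 5.4 all point the same way. App orientation takes place at screening (6.1 and 6.2), and type of smartphone is a baseline variable (7.4.5), so a patient without a device would hardly pass unnoticed. On that view this is a misplaced list item with a documentation consequence, and the loss of endpoints is hypothetical.

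Most of that is fair. The item is very probably a drafting slip, enrolment of the wrong population is unlikely, and the case should not rest on the endpoint-loss scenario. It does not remove the defect. Orientation and baseline variables are not entry criteria, and the text that screening staff and monitors must work from still says the reverse of what is meant.

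A second point concerns inclusion criterion 3. It may not cover app use, since 5.2 leaves participants free to use the app at their leisure. The result that only willing people without a device remain is therefore conditional. The conclusion does not depend on it, because the intended group is excluded either way.

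The item cannot be put down to text extraction. The list runs from 1 to 5 unbroken and the sentence is complete. Nor is eligibility a matter left to a statistical analysis plan.

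**Conclusion.** The concern holds. Exclusion criterion 4 is an inclusion condition in the wrong list and contradicts the protocol's own objective, design, primary endpoints and intervention procedures. Followed exactly, it selects a population with no overlap with the intended one and effectively empties five of the eight listed primary endpoints. Applied in reverse, as is likely, it leaves up to all 50 participants meeting a written exclusion criterion, and someone without a suitable device faces no written exclusion.

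The zero overlap needs no assumption beyond reading the any-item rule as it stands. The harm to expect is to the eligibility record and to compliance with the approved protocol, not bias in an estimate. It must be fixed because the text is operative and affects every intended participant.

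**What to change.** Delete item 4 from 4.4.2, so that pregnancy becomes item 4, and add the same sentence to 4.4.1 as item 8: "Willing to download and use the Epic Care Companion app and has a suitable mobile device to do this". The wording needs no change once it stands in the inclusion list. If the sponsor prefers to keep it as an exclusion, it must be negated with *or*: not willing to use the app, or without a suitable device.

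Check the screening form, which is not among the documents, and correct it if it repeats the error. If enrolment has begun, document how the criterion was applied to everyone already screened. Optionally, record unwillingness to use the app and lack of a device as separate reasons among the screen-failure details collected under 4.6.

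The cost is a one-line amendment with ethics board approval and, if needed, a form edit. Sample size, visits and analyses do not change.

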4.5 Lifestyle Considerations

None

4.6 Screen Failures

We will collect screen failures demography, screen failure details, eligibility criteria, and any serious adverse events (SAE).

4.7 Participant Withdrawal Criteria

4.7.1 When and How to Withdraw Participants

Participants are free to withdraw from participation in the clinical trial at any time. An investigator may discontinue or withdraw a participant from the clinical trial for the following reasons:

- Pregnancy;
- If any adverse event (AE), laboratory abnormality, or other medical condition or situation occurs such that continued participation in the clinical trial would not be in the best interest of the participant;
- Disease progression which requires discontinuation of the study intervention;
- If the participant meets an exclusion criterion (either newly developed or not previously recognized) that precludes further study participation

MLHC study

The reason for participant discontinuation or withdrawal from the study will be recorded within the participant's research record, and/or legal health record.

4.7.2 Follow -up for Withdrawn Participants

If a participant withdraws consent, they can also request the withdrawal of their data and/or biological specimens subject to any research-specific restrictions, if applicable. Once withdrawn from the clinical trial, no further research procedures or evaluations will be performed, or additional research-specific data collected on the participant. Reasonable effort will be made to obtain permission to document the reason for withdrawal.

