4.7.3 Early Termination Visit

If a participant withdraws from the clinical trial, an Early Termination Visit will be arranged if possible with study staff. This will include:

- Assessment of new and ongoing AEs;
- Assessment of any complications following the study intervention;
- Performance of other relevant study-related procedures.

The PI and/or QI will ensure the participant is appropriately transitioned/followed for any additional care as required.

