4.7.4 Participants who are Lost to Follow -up

A participant will be considered lost to follow-up if they fail to return for 2 scheduled visits and is unable to be contacted by the research team.

The following actions will be taken if a participant fails to attend a required study visit:

- The research team will attempt to contact the participant and reschedule the missed visit within 2 weeks, counsel the participant on the importance of maintaining the assigned visit schedule, and reconfirm whether the participant wishes to and/or should continue in the clinical trial.
- Before a participant is deemed lost to follow-up, the research team will make every
 effort to regain contact with the participant (where possible, three telephone calls
 and, if necessary, a certified letter to the participant's last known mailing address or
 local equivalent methods). These contact attempts should be documented in the
 participant's research record and/or legal health record.
- Should the participant continue to be unreachable, they will be considered to have withdrawn from the clinical trial with a primary reason of lost to follow-up.

MLHC study

5.0 **STUDY INTERVENTION**

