6.0 RESEARCH PROCEDURES

6.1 Research Visits

- Pre-Screening Visit / Screening Visit (virtual or in-person)
 - Informed consent
 - Review of eligibility criteria
 - Orientation to the Epic Care Companion MLHC companion app
 - This visit will be performed by study staff (research assistant, or study investigators)
- Baseline Visit (virtual)
 - Collection of baseline outcome data
 - This visit will be performed by CREs as part of the MLHC program, study staff (research assistant, or study investigators) will confirm data collection and if needed supplement data collection using Epic or by contacting the participant

MLHC study

- Delivery of MLHC program 6 virtual sessions over 12 weeks, delivered by CREs, no outcome collection during this phase of the study
- Follow-up Visit at 3 months post baseline (virtual)
 - o Collection of follow-up outcome data
 - This visit will be performed by CREs as part of the MLHC program, study staff (research assistant, or study investigators) will confirm data collection and if needed supplement data collection using Epic or by contacting the participant
- Follow-Up Visit at 6 months post baseline (virtual)
 - o Collection of follow-up outcome data
 - This visit will be performed by CREs as part of the MLHC program, study staff (research assistant, or study investigators) will confirm data collection and if needed supplement data collection using Epic or by contacting the participant

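### The stop on data collection in Protocol 4.7.2 is not limited to withdrawal of consent and conflicts with the exit visit in 4.7.3, and 4.7.4 contains two different lost-to-follow-up rules

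*Protocol*

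**What the plan says.** Protocol 4.7.2 begins with a participant who withdraws consent and may ask for their data to be withdrawn. It then sets a general rule: "Once withdrawn from the clinical trial, no further research procedures or evaluations will be performed, or additional research-specific data collected on the participant". It closes by making a record of the reason subject to the participant's permission.

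Protocol 4.7.3 says: "If a participant withdraws from the clinical trial, an Early Termination Visit will be arranged if possible with study staff". That visit covers new and ongoing adverse events, complications, and "Performance of other relevant study-related procedures".

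Protocol 4.7.1 lets the investigator withdraw a participant for, among other reasons, an adverse event or other medical condition, or progression of disease. It requires the reason to be recorded.

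Protocol 4.7.4 defines lost to follow-up by two conditions together, namely that participants "fail to return for 2 scheduled visits and is unable to be contacted by the research team". The action list below it has a different trigger: "The following actions will be taken if a participant fails to attend a required study visit". If rescheduling and the contact attempts fail, "they will be considered to have withdrawn from the clinical trial with a primary reason of lost to follow-up".

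Protocol 6.1 and 6.2 place two outcome visits after baseline, at 3 and 6 months. The six sessions fall within 12 weeks and collect no outcomes. Sections 3.3 and 6.1 name Epic chart review as an outcome source beside the educators' form.

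**The concern.** The protocol uses one word, withdrawn, for people in different positions: those who revoke consent, those whom the investigator takes out, and those who cannot be reached. Section 4.7.2 applies the same consequence to all of them.

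Only the first group has asked for data collection to end. Membership of the second is tied to how the patient is doing, because adverse events and progression are listed reasons. If collection stops there, the missing 3- and 6-month values are likely to be worse than those observed.

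The variables at stake are health service use and exacerbations. These are secondary endpoints in 3.3 and also the safety signals that 7.4.4 and 8.5 rely on. Much of this could be read from Epic without contacting the participant. An analysis plan cannot recover data that the protocol told staff not to collect.

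Separately, staff cannot follow 4.7.2 and 4.7.3 literally for the same participant, and two people applying 4.7.4 could give the same participant different dispositions.

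**Working it through.** The protocol states no figure on this point, so there is none to reproduce. The check sets the rules side by side, then counts visits.

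**1. Reach of the stop on data**

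| Route out of the trial | Consent withdrawn? | 4.7.2 as written | What else the protocol says |
|---|---|---|---|
| Participant withdraws consent | Yes | Stop | 4.7.3 arranges an exit visit if possible |
| Investigator withdraws for adverse event or progression (4.7.1) | Not necessarily | Stop | 7.4.4 and 8.5 look for safety signals at 3 and 6 months |
| Unreachable, classed as withdrawn (4.7.4) | No | Stop | 3.3 and 6.1 allow outcome data from Epic without contact |

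Row 1 is the direct conflict: withdrawal leads both to no further evaluation and to an evaluation visit. Rows 2 and 3 are where the stop reaches people who have not revoked consent. Extracting study outcomes from Epic is research data collection, so it falls under the plain words of 4.7.2 although chart review is not named there.

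Section 4.7.3 does not fill the gap. Beyond adverse events and complications it names no outcome scale, only unspecified procedures.

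**2. What remains covered**

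Under Protocol 8.1, deaths and adverse events after discontinuation that may reasonably be related to the trial are still notified to the sponsor. What goes uncollected is the systematic record: service use, exacerbations and scores at the remaining visits, and later events judged unrelated.

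**3. Lost-to-follow-up count**

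Inputs are the outcome visits at months 3 and 6 (6.1, 6.2) and the threshold of two missed visits (4.7.4).

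- Contact lost before month 3: months 3 and 6 are missed, 2 ≥ 2, and the definition can be met.
- Contact lost after attending through month 3: only month 6 is missed, 1 < 2, and the definition cannot be met. Counting sessions as visits does not help, because they are over by week 12. The exceptions are a session missed earlier, or a rescheduled month-6 visit counted as a second one.
- Under the action list, the same late participant is labelled lost to follow-up after one missed visit.

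If 5% to 30% of the 50 participants were lost late (assumed), 50 × 0.05 = 2.5 to 50 × 0.30 = 15 people would be labelled differently under the two rules.

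**4. Illustration of selective loss**

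Shift in the observed mean = d × (mean of those observed − mean of those missing), where d is the fraction missing. Both inputs are assumed, since the protocol gives neither.

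| d | gap 1 CAT point | gap 2 | gap 4 |
|---|---|---|---|
| 0.10 | 0.1 | 0.2 | 0.4 |
| 0.20 | 0.2 | 0.4 | 0.8 |
| 0.30 | 0.3 | 0.6 | 1.2 |

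This is the effect of all selective loss on a questionnaire score. Only part of it would come from 4.7.2.

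**The case against.** The strongest reply is that 4.7.2 opens with withdrawal of consent and ends by seeking permission, so its middle sentence may be meant only for that case. The exit visit can then be read as a last assessment before collection stops. Nothing in 4.7 makes stopping sessions a withdrawal, and the 3- and 6-month visits are timed from baseline whether or not sessions were completed. The affected clinical endpoints are secondary, in a pilot with no hypotheses (7.1) and no powering for clinical outcomes (7.2).

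This shows that a workable reading exists, not that the text requires it. The rule is worded for anyone withdrawn from the trial, and 4.7.1 and 4.7.4 use that term for people who have not revoked consent. The limited stakes are a fair point and bear on priority.

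A reader might also infer more than the protocol supports:

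- *Late losses are never counted, or disposition is lost.* The action list in 4.7.4 gives the lost-to-follow-up label after one missed visit, contact attempts are documented, and 4.7.1 requires the reason to be recorded. The fault is two inconsistent rules. Contact attempts start at the first missed visit, so the threshold does not decide whether month-6 data are sought.
- *Retention looks better than it is.* Programme completion is counted over all who started, so those who stop stay in the denominator. Loss after month 3 comes after the sessions have ended.
- *The clinical effect is overstated by a known amount because of 4.7.2.* Section 7.3 separately limits the clinical analysis to completers with follow-up. Bias from leaving out non-completers arises mainly there, and repairing 4.7 alone would not bring them back.
- *Adverse events stop being recorded.* Those that may be related are still notified under 8.1.

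**Conclusion.** The point holds in a limited form. Sections 4.7.2 and 4.7.3 give opposite instructions on withdrawal. The stop on data in 4.7.2 extends, as written, to investigator withdrawals and unreachable participants. Following it can lose chart-review outcomes and safety signals in a way related to prognosis. Section 4.7.4 also contains two lost-to-follow-up rules that disagree for anyone who attends through month 3 and misses only month 6; that is a matter of classification.

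The size cannot be derived from the protocol, which states neither a withdrawal rate nor a difference between those kept and those lost. The shift of 0.1 to 1.2 CAT points rests on assumed values of 10% to 30% missing and a gap of 1 to 4 points, and shows scale only. The consequence falls on secondary clinical endpoints and safety follow-up, not on the programme-completion ratio. It is worth correcting before enrolment, because the uncollected data cannot be replaced later and 7.2 intends the results to inform a controlled trial.

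**What to change.** Four changes to section 4.7, all about data collection:

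1. Confine the stop in 4.7.2 to withdrawal of consent.
2. State that participants who stop sessions, are withdrawn by the investigator or cannot be reached, but have not withdrawn consent, stay in the 3- and 6-month data collection. For unreachable participants this means at least Epic chart review.
3. Reconcile 4.7.3 with 4.7.2 by stating that, for a participant withdrawing consent, any exit assessment takes place before the withdrawal takes effect and only with their agreement.
4. Define lost to follow-up separately for each outcome visit: the visit was missed, was not completed within the existing two-week rescheduling period, and the participant remained unreachable after the contact steps already listed. Remove the two-visit threshold.

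If programme non-completers are to enter the clinical analysis, the completer-only population in 7.3 must change as well. That is a separate decision.

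The cost is protocol and consent-form wording and a few extra chart reviews by existing staff.
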